9.4.4. Other Safety Analyses

Clinical Laboratory Tests

Laboratory data (adult only) will be summarized by group and overall by type of laboratory test. Reference ranges and markedly abnormal results (specified in the SAP) will be used in the summary of laboratory data. Descriptive statistics will be calculated for all laboratory analyte at each time point. A listing of participants with any laboratory results outside the reference ranges will be provided. A listing of participants with any markedly abnormal laboratory results will also be provided.

Vital Signs

Vital signs including body temperature, pulse/heart rate, respiratory rate, and blood pressure (adults only: systolic and diastolic) and blood oxygen saturation will be summarized over time by group and overall, using descriptive statistics and/or graphically. The percentage of participants with values beyond clinically important limits (specified in the SAP) will be summarized by group and overall.

Physical Examinations

Physical examination findings will be summarized at baseline (adults) and at each timepoint for neonates/infants by group and overall. A listing of abnormalities will be made for each scheduled time point.

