- z. In the situation of a completion/ termination of the pregnancy before the completion of the applicable Study Period visits, PP1 (Visit 9) is to be completed. The participant should then follow the visits scheduled in the 'Study Period' up to Visit 5 (meaning all scheduled visits in this period except for the monthly phone calls Visits 6 8) AND the 'Follow up' section of the schedule of activities (Visits 10 12). Additional guidance if the pregnancy is completed/ terminated before the pre partum visits are completed is provided in Appendix 10.13.
- aa. Body temperature will be measured preferably via the oral route, or in accordance with the local standard of care.
- bb. History of COVID 19 vaccination (name/manufacturer of the vaccine and date of administration) ≥ 4 months prior to the study vaccine will be reported in the eCRF.
- cc. Laboratory assessments performed at Visits 4 and 5 are optional. If the outcome from the laboratory assessment at Visit 3 show abnormal results that are considered clinically significant, then an on site visit should be performed. In this case, an additional sample should be taken for further assessment 7 days later and until normalization of the readings, at the discretion of the investigator and targeted physical examinations and vital signs should be collected. If the outcome from the laboratory assessment at Visit 3 show normal results, only a safety phone call is required (no physical examinations and vital signs needed).
- dd. With only 1 participant in this subset at the time of writing this Protocol Amendment 7, PBMC sampling will be removed from the study as of Protocol Amendment 7 approval.
- ee. The Follow up safety assessments for adults at the end of the study visit (no.12) may be performed simultaneously with postnatal (PN 12 months) follow up safety visit (no. 14) as feasible.

AE adverse event; AESI adverse event of special interest; COVID 19 coronavirus disease 2019; d day(s); eCOA electronic clinical outcome assessment; eDC electronic data capture; FU follow up; ICF informed consent form; MAAE medically attended adverse event; m months; PBMC peripheral blood mononuclear cell; PP postpartum; SAE serious adverse event; SIC Symptoms of Infection with Coronavirus 19; SARS CoV 2 severe acute respiratory syndrome coronavirus2.

1.3.1.1. Vaccine Naïve Adult Participants (Group 4, Including Sentinel and Safety Cohorts): Booster Vaccination Visits

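### Day 15 by-visit laboratory and vital-sign summaries can rest on women re-sampled because their Day 8 result was abnormal

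*Protocol*

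**What the plan says.** Section 9.4.4 (Other Safety Analyses) makes two commitments, neither limited to visits at which everyone is measured. For laboratory data: "Descriptive statistics will be calculated for all laboratory analyte at each time point". For vital signs: they "will be summarized over time by group and overall, using descriptive statistics and/or graphically". It also promises listings of out-of-range and of markedly abnormal laboratory results.

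The schedules qualify who is measured. In Section 1.3.1 (Group 4), footnote cc says "Laboratory assessments performed at Visits 4 and 5 are optional". If the Visit 3 (Day 8) laboratory results "show abnormal results that are considered clinically significant, then an on site visit should be performed", and "an additional sample should be taken for further assessment 7 days later and until normalization of the readings", together with a targeted examination and vital signs. If Visit 3 is normal, "only a safety phone call is required (no physical examinations and vital signs needed". Footnote bb in Section 1.3.2 repeats this for Groups 1-3. Visit 4 is Day 15 and Visit 5 is Day 29.

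**The concern.** Set together, these rules make membership of the Day 15 column depend on the Day 8 result. The women who must be measured at Day 15 are those already judged abnormal; the rest may be measured or not. A mean or median from such a group need not describe vaccinated women in general.

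The setting makes this worth correcting. The study has no placebo group, so a reader cannot separate a selected column from a vaccine effect. Platelet count is in the local panel, thrombocytopenia is a suspected event of special interest, and Section 2.3.1 places thrombosis with thrombocytopenia at about three weeks after vaccination. Enrolment has been stopped early, so a few re-sampled women could supply a whole group's Day 15 column. Section 9.5 allows any analysis to be used in regulatory submissions.

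**Working it through.** **Who is measured, visit by visit**

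- *Day 15 laboratory tests and vital signs.* The footnotes require both only after a clinically significant abnormal Day 8. Section 8.2.1 lists targeted examinations at Day 8 and Day 29 but not Day 15, which fits Day 15 being conditional. The vital-signs row of the schedule does mark Day 15 without the footnote, so row and footnote disagree.
- *Day 29 laboratory tests.* Optional under the same footnotes. However, all women are due on site for stored plasma and serum, humoral serum and N-serology, none marked optional. Selection depends on how many women with a normal Day 8 are also tested.
- *Day 29 vital signs.* The row is again marked without the footnote, Section 8.2.1 schedules a Day 29 examination without condition, and the blood draws bring women to the site. The phone-call clause conflicts with these; selection is not shown.

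**Size under assumed inputs**

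The plan gives no figure to reproduce. Take bivariate-normal values at Day 8 and the later visit with no vaccine effect. Let p be the share abnormal at Day 8 (one-sided cut-off c), ρ the correlation between visits, and q the share of Day-8-normal women sampled anyway. All three are assumptions. Shifts are towards abnormality, in SD units.

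*Case A: selection on the analyte being summarised.*

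Shift = ρ·φ(c)·(1 − q) / [p + q(1 − p)]

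With p = 0.05, c = 1.645 and φ(c) = 0.1031. At q = 0, φ(c)/p = 2.06, so:

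- ρ = 0.3: 0.62 SD; tabulated abnormal rate 14% against a true 5%
- ρ = 0.5: 1.03 SD; 24% against 5%
- ρ = 0.8: 1.65 SD; 50% against 5%

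The rates are P(both visits abnormal)/p from the bivariate normal. With ρ = 0.5 and some normal women sampled:

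- q = 0.10: 0.5 × 0.1031 × 0.90 / 0.145 = 0.32 SD; rate 11%
- q = 0.25: 0.5 × 0.1031 × 0.75 / 0.2875 = 0.13 SD; rate 7.5%
- q = 0.50: 0.5 × 0.1031 × 0.50 / 0.525 = 0.05 SD; rate 5.9%
- q = 1: 0 SD; rate 5%

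*Case B: any abnormal analyte triggers a redraw of the whole panel.* Table 6 lists 16 blood analytes (10 haematology and coagulation, 6 chemistry). Treat them as independent, each abnormal with p = 0.01, and q = 0.

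Share redrawn = 1 − 0.99^16 = 0.149, about 3 of 22 women or 6 of 40.

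Shift per analyte = ρ·φ(c)·0.99^15 / 0.149, with c = 2.326 and φ(c) = 0.0267, which is ρ × 0.154. That gives 0.05, 0.08 and 0.12 SD at ρ = 0.3, 0.5 and 0.8; simulation agrees. The share with any abnormal analyte at the later visit is 19%, 24% and 45%, against a true 15%.

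Case B is nearer the footnotes' trigger, which is not tied to one analyte. Case A shows what can happen to the analyte that caused the redraw.

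**The case against.** Four arguments carry weight.

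- *Detail belongs in the SAP.* Section 9.4 calls itself a summary, defers technical detail, and allows some endpoints to be given only as listings because of the limited sample size. Section 9.4.4 already promises listings of abnormal results. But the listing clause is discretionary and concerns sample size, not conditional sampling, while 9.4.4 states its own rule without exception: every analyte, each time point.
- *Nothing forbids testing women with a normal Day 8.* Table 1 budgets up to seven safety samples per woman, which covers every laboratory cell, Day 15 and Day 29 included. This stands: the summaries can be biased, not must be.
- *The tables are descriptive.* No hypothesis is tested, laboratory means are not a primary endpoint, clinically relevant changes are recorded as adverse events, and low platelet counts are reported as suspected events of special interest. This limits the consequence to how safety tables are read.
- *A column of one or two women is recognisable from its n.* Partly true, but n alone does not say why those women were sampled.

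A reader might infer that Day 29 is distorted in the same way, vital signs included. The on-site draws and Section 8.2.1 do not support that. A reader might also expect by-visit abnormality percentages or changes from baseline to be affected. Section 9.4.4 promises neither for laboratory tests; its vital-sign percentage is given per group and for all women together, with no mention of visit. The abnormality rates in the working therefore matter only if such tables are produced.

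**Conclusion.** The point holds for Day 15. Followed as written, 9.4.4 treats Day 15 as an ordinary time point, although the footnotes require data there only from women with a clinically significant abnormal Day 8 result. It holds in weaker form for Day 29 laboratory tests, to an unknown degree, and is not established for Day 29 vital signs.

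The size cannot be taken from the documents. It runs from about 0.05-0.12 SD per analyte under a 16-analyte trigger to about 0.6-1.65 SD under same-analyte selection, and falls to zero if all women are sampled. These figures rest on assumed abnormality shares, correlations and sampling of normal women, on normality and, in Case B, on independent analytes. A shift of a full SD or more should not be read as the expected result, since it needs selection on the summarised analyte with almost no other women tested. The effect is on descriptive safety tables in an uncontrolled study; no test or primary endpoint changes.

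**What to change.** In Section 9.4.4:

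- Exclude conditional Day 15 and repeat laboratory and vital-sign values from the by-visit descriptive statistics. Present them as listings with number sampled, reason for sampling and number vaccinated.
- Show Day 29 laboratory summaries only with the number sampled out of the number vaccinated, split by reason (scheduled or optional, versus triggered by Day 8).
- Add a worst-post-baseline shift table from Day 1.

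In Sections 1.3.1 and 1.3.2, the phone-call-only clause of footnotes cc and bb must be reconciled with the on-site Day 29 draws, the unfootnoted vital-signs row and Section 8.2.1. Which rule applies is for the sponsor to settle.

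The delivery visit should not be described as measured in everyone: footnote d says blood samples are not expected when delivery is at a hospital where site staff lack privileges.

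The cost is wording and table shells, with no new data. The Day 15 column leaves the by-visit tables.

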9.5. Planned Analyses

The SAP will describe the planned primary analysis and final analysis, in greater detail. The results of any analysis may be used for regulatory submissions.

Unplanned interim analyses may be as required or if requested by health authorities.

The IDMC will review safety and reactogenicity data as described in Section [10.3.6](#).

9.5.1. Primary Analysis

The primary analysis of safety and immunogenicity will be performed when all adult participants have completed the visit that takes place approximately 42 days postpartum in all groups or if adult participants are discontinued earlier. The analysis will include safety (AEs, SAEs, and pregnancy outcomes) and immunogenicity data (S-ELISA and VNA) for all adult participants and neonates/infants and in cord blood at the time of delivery. The primary analysis will include all data up to and including the Day 42 postpartum follow-up visit. The results of this analysis may be used for regulatory submissions.

9.5.2. Final Analysis

The final analysis will be performed when all adult participants and all neonates/infants have completed the final visit per the Schedules of Activities in Section [1.3](#). Analysis will include safety (AEs, SAEs, and pregnancy outcomes) and immunogenicity data. Booster dose effect will be evaluated on safety and immunogenicity.

The SAP will describe the planned analyses in greater detail.

Note: Interim analyses may be performed as required or if requested by health authorities.

10. SUPPORTING DOCUMENTATION AND OPERATIONAL CONSIDERATIONS

10.1. Appendix 1: Abbreviations

Ad26	adenovirus type 26
AdVAC [®]	adenoviral vaccine (vector platform)
AE	adverse event
AESI	adverse event of special interest
ALT	alanine aminotransferase
Anti-PF4	anti-platelet factor 4
AST	aspartate aminotransferase
BMI	body mass index
BUN	Blood Urea Nitrogen
CD	cluster of differentiation
CDC	Centers for Disease Control and Prevention
CLS	Capillary leak syndrome
COPD	chronic obstructive pulmonary disease
COVID-19	coronavirus disease-2019
CPK	creatine phosphokinase
eCRF	Electronic case report form(s)
DBL	data base lock
DNA	deoxyribonucleic acid
DTaP	Diphtheria toxoid, Tetanus toxoid, and acellular Pertussis
DVT	deep vein thrombosis
eCOA	electronic clinical outcome assessment
eDC	electronic data capture
ePRO	electronic patient-reported outcomes
EF-PPND	embryofetal and pre-and postnatal development toxicity
ELISA	enzyme-linked immunosorbent assay
ELISpot	enzyme-linked immunospot
ERD	enhanced respiratory disease
FAS	Full Analysis Set
Fc	crystallizable fragment
FDA	Food and Drug Administration
FI	formalin-inactivated
GCP	good clinical practice
GD	gestation day
GLP	good laboratory practice
GMC	Geometric mean concentration
GMT	Geometric mean titer
HCP	health care professional
HELLP	hemolysis elevated liver enzymes and low platelets
HIT	heparin-induced thrombocytopenia
HIV	human immunodeficiency virus
IB	investigator's brochure
ICF	informed consent form
ICS	intracellular cytokine staining
ICH	International Conference on Harmonization
ICU	intensive care unit
IDMC	Independent Data Monitoring Committee
IEC	Independent Ethics Committee
IFN- γ	interferon gamma
Ig	immunoglobulin
IL	interleukin
IM	intramuscular
IPPI	Investigational Product Preparation Instructions
IRB	Institutional Review Board
IWRS	interactive web response system

MAAE	Medically-attended adverse event
MedDRA	Medical Dictionary for Regulatory Activities
MERS (-CoV)	Middle East respiratory syndrome (coronavirus)
MIS-C	Multisystem Inflammatory Syndrome in Children
N	nucleocapsid
ObsRO	Observer-reported outcomes
PBMC	peripheral blood mononuclear cell
PedSIC	Pediatric Symptoms of Infection with Coronavirus-19
PI	principal investigator
PPI	per protocol immunogenicity
PQC	product quality complaint
RNA	ribonucleic acid
RSV	respiratory syncytial virus
RT-PCR	real-time reverse-transcriptase polymerase chain reaction
S	spike
SAE	serious adverse event
SAP	statistical analysis plan
SARS	severe acute respiratory syndrome
SARS-CoV(-2)	severe acute respiratory syndrome coronavirus(-2)
SIC	Symptoms of Infection with Coronavirus-19
SIPPM	site investigational product and procedures manual
SpO ₂	oxygen saturation
SRP/S	study responsible physician/scientist
SUSAR	suspected unexpected serious adverse reaction
TTS	Thrombosis with thrombocytopenia syndrome
Th	T helper
Th1/Th2	T helper cell subset(s)
TNF- α	tumor necrosis factor alpha
ULN	upper limit of the normal range
US	United States
VAERD	vaccine-associated enhanced respiratory disease
VSD	Vaccine Safety Datalink
VNA	virus neutralization assay
vp	virus particle
WBC	white blood cell
WHO	World Health Organization

Definition of Terms

COVID-19	COVID-19 is the disease caused by the virus SARS-CoV-2. COVID-19 refers to SARS-CoV-2 infection with symptoms, and can range from mild to severe disease, the latter including pneumonia, severe acute respiratory syndrome, multiorgan failure, and death (US FDA May 2020 , US FDA June 2020).
eCOA	Electronic Clinical Outcome Assessment. An umbrella term encompassing different types of outcomes assessments, which may include the COVID-19 signs and symptoms surveillance question, SIC (as an ePRO for adults), PedSIC (as an ObsRO for neonates/infants) and the reactogenicity diary (to record vaccine reactogenicity) in adults. Note: should the eCOA not be available, paper format will be used to collect the data.
ePRO	The electronic technology used to collect the patient-reported outcome data. PROs are reports that come directly from the participant without interpretation by clinician or anyone else. This includes the SIC questionnaire and the recording of pulse oximetry results.
reactogenicity diary	Used to record solicited signs and symptoms by the participants.

Electronic source system	Contains data traditionally maintained in a hospital or clinic record to document medical care or data recorded in a CRF as determined by the protocol. Data in this system may be considered source documentation.
ObsROs	Observer-reported Outcomes. Used to collect the observer-reported outcome data. ObsROs are reports that come directly from the legal guardian/caregiver without interpretation by a clinician or anyone else. This includes the PedSIC questionnaire and the recording of pulse oximetry results.

10.2. Appendix 2: Clinical Laboratory Tests

10.2.1. Protocol Required Safety Laboratory Assessments - Adult Participants

The following Hematology, Chemistry and Urinalysis tests will be performed locally within 72 hours of blood sample collection, according to the Schedules of Activities (Section 1.3).

Table 6: Protocol Required Safety Laboratory Assessments to be Performed Locally

Laboratory Assessments	Parameters		
Hematology	Platelet count Hemoglobin	Prothrombin time Activated partial thromboplastin time	White Blood Cell (WBC) count with Differential: Neutrophils Lymphocytes Monocytes Eosinophils Basophils
	Note: A WBC evaluation may include any abnormal cells, which will then be reported by the laboratory. In addition, any other abnormal cells in a blood smear will also be reported.		
Clinical Chemistry	Sodium Potassium Blood urea nitrogen (BUN) Creatinine Aspartate aminotransferase (AST) Alanine aminotransferase (ALT)		
Routine Urinalysis	Dipstick* Glucose Protein Blood	Sediment (if dipstick result is abnormal)	
	If dipstick result is abnormal, microscopy will be used to measure sediment. *Urine dipstick analyses will be performed locally and will be confirmed by the central laboratory if the local result is abnormal.		

Table 7: Additional Laboratory Assessments to be Performed as Required

Laboratory Assessments	Parameters	Timepoints
Testing done locally		
Standard Laboratory Assessments	
 Urine pregnancy testing 	Pre-vaccination at the Booster Vaccination Visit
Testing done centrally		
Hematology Clinical Laboratory Assessments of Coagulation-related parameters (Section 8.2.3.1)	Participants with a suspected AESI: 
 Serum/plasma samples for coagulation-related assays such as but not limited to: 
 Activated partial thromboplastin time Prothrombin time 	Based on the clinical evaluation of the suspected AESI (eg, whether thrombocytopenia is observed in conjunction with a thrombotic event), all or some of these tests may be conducted on samples obtained as part of the AESI investigation. Similar samples from appropriate controls (from vaccinated participants who did not experience an

Laboratory Assessments	Parameters	Timepoints
	
 ○ International normalized ratio ○ Fibrinogen ○ D-dimer levels ○ Lupus anticoagulant ○ Anti-cardiolipin antibody ○ Beta-2 glycoprotein ○ HIT/anti-PF4 Antibodies, IgG (HIT assay) ○ Platelet activation assay (if HIT/anti-PF4 antibodies is positive) ○ Homocysteine ● ADAMTS13 Activity and Inhibitor Profile 	
AESI) within the study may be used as part of investigation of AESIs.
 
 ● All or some of these tests may be conducted to assess hematology laboratory parameters in a subset of participants, and the extent to which levels of these factors in peripheral blood fluctuate pre-and post-vaccination with Ad26.COV2.S.

Laboratory abnormalities in adult participants are listed in Section 10.5.

10.3. Appendix 3: Regulatory, Ethical, and Study Oversight Considerations

10.3.1. Regulatory and Ethical Considerations

Investigator Responsibilities

The investigator is responsible for ensuring that the study is performed in accordance with the protocol, current International Conference on Harmonization (ICH) guidelines on Good Clinical Practice (GCP), and applicable regulatory and country-specific requirements.

GCP is an international ethical and scientific quality standard for designing, conducting, recording, and reporting studies that involve the participation of human participants. Compliance with this standard provides public assurance that the rights, safety, and well-being of study participants are protected, consistent with the principles that originated in the Declaration of Helsinki, and that the study data are credible.

Protocol Amendments

Neither the investigator nor the sponsor will modify this protocol without a formal amendment by the sponsor. All protocol amendments must be issued by the sponsor, and signed and dated by the investigator. Protocol amendments must not be implemented without prior IEC/IRB approval, or when the relevant competent authority has raised any grounds for non-acceptance, except when necessary to eliminate immediate hazards to the participants, in which case the amendment must be promptly submitted to the IEC/IRB and relevant competent authority. Documentation of amendment approval by the investigator and IEC/IRB must be provided to the sponsor. When the change(s) involve only logistic or administrative aspects of the study, the IEC/IRB (where required) only needs to be notified.

During the course of the study, in situations where a deviation from the protocol is unavoidable, the investigator or other physician in attendance will contact the appropriate sponsor representative listed in the Contact Information page(s), which will be provided as a separate document. Except in emergency situations, this contact should be made before implementing any deviation from the protocol. In all cases, contact with the sponsor must be made as soon as possible to discuss the situation and agree on an appropriate course of action. The data recorded in the eCRF and source documents will reflect any deviation from the protocol, and the source documents will describe this deviation and the circumstances requiring it.

Regulatory Approval/Notification

This protocol and any amendment(s) must be submitted to the appropriate regulatory authorities in each respective country, if applicable. A study may not be initiated until all local regulatory requirements are met.

Required Prestudy Documentation

The following documents must be provided to the sponsor before shipment of study vaccine to the study site:

- Protocol and amendment(s), if any, signed and dated by the PI
- A copy of the dated and signed (or sealed, where appropriate per local regulations), written IEC/IRB approval of the protocol, amendments, ICF, any recruiting materials, and if applicable, participant compensation programs. This approval must clearly identify the specific protocol by title and number and must be signed (or sealed, where appropriate per local regulations) by the chairman or authorized designee
- Name and address of the IEC/IRB, including a current list of the IEC/IRB members and their function, with a statement that it is organized and operates according to GCP and the applicable laws and regulations. If accompanied by a letter of explanation, or equivalent, from the IEC/IRB, a general statement may be substituted for this list. If an investigator or a member of the study site personnel is a member of the IEC/IRB, documentation must be obtained to state that this person did not participate in the deliberations or in the vote/opinion of the study
- Regulatory authority approval or notification, if applicable
- Signed and dated statement of investigator (eg, Form FDA 1572), if applicable
- Documentation of investigator qualifications (eg, curriculum vitae)
- Completed investigator financial disclosure form from the PI, where required
- Signed and dated Clinical Trial Agreement, which includes the financial agreement
- Any other documentation required by local regulations

The following documents must be provided to the sponsor before enrollment of the first participant:

- Completed investigator financial disclosure forms from all subinvestigators
- Documentation of subinvestigator qualifications (eg, curriculum vitae)
- Name and address of any local laboratory conducting tests for the study, and a dated copy of current laboratory normal ranges for these tests, if applicable
- Local laboratory documentation demonstrating competence and test reliability (eg, accreditation/license), if applicable

Independent Ethics Committee or Institutional Review Board

Before the start of the study, the investigator (or sponsor where required) will provide the IEC/IRB with current and complete copies of the following documents (as required by local regulations):

- Final protocol and, if applicable, amendments
- Sponsor-approved ICF (and any other written materials to be provided to the participants)
- IB (or equivalent information) and amendments/addenda
- Sponsor-approved participant recruiting materials
- Information on compensation for study-related injuries or payment to participants for participation in the study, if applicable

- Investigator's curriculum vitae or equivalent information (unless not required, as documented by the IEC/IRB)
- Information regarding funding, name of the sponsor, institutional affiliations, other potential conflicts of interest, and incentives for participants
- Any other documents that the IEC/IRB requests to fulfill its obligation

This study will be undertaken only after the IEC/IRB has given full approval of the final protocol, amendments (if any, excluding the ones that are purely administrative, with no consequences for participants, data or study conduct, unless required locally), the ICF, applicable recruiting materials, and participant compensation programs, and the sponsor has received a copy of this approval. This approval letter must be dated and must clearly identify the IEC/IRB and the documents being approved.

During the study the investigator (or sponsor where required) will send the following documents and updates to the IEC/IRB for their review and approval, where appropriate:

- Protocol amendments (excluding the ones that are purely administrative, with no consequences for participants, data or study conduct)
- Revision(s) to ICF and any other written materials to be provided to participants
- If applicable, new or revised participant recruiting materials approved by the sponsor
- Revisions to compensation for study-related injuries or payment to participants for participation in the study, if applicable
- New edition(s) of the IB and amendments/addenda
- Summaries of the status of the study at intervals stipulated in guidelines of the IEC/IRB (at least annually)
- Reports of AEs that are serious, unlisted/unexpected, and associated with the study vaccine
- New information that may adversely affect the safety of the participants or the conduct of the study
- Deviations from or changes to the protocol to eliminate immediate hazards to the participants
- Report of deaths of participants under the investigator's care
- Notification if a new investigator is responsible for the study at the site
- Development Safety Update Report and Line Listings, where applicable
- Any other requirements of the IEC/IRB

For all protocol amendments (excluding the ones that are purely administrative, with no consequences for participants, data or study conduct), the amendment and applicable ICF revisions must be submitted promptly to the IEC/IRB for review and approval before implementation of the change(s).

At least once a year, the IEC/IRB will be asked to review and reapprove this study, where required.

At the end of the study, the investigator (or sponsor where required) will notify the IEC/IRB about the study completion.

Country Selection

This study will only be conducted in those countries where the intent is to launch or otherwise help ensure access to the developed product if the need for the product persists, unless explicitly addressed as a specific ethical consideration in Section 4.1.1.

Other Ethical Considerations

For study-specific ethical design considerations, refer to Section 4.1.1.

